5 STUDY ENROLLMENT AND WITHDRAWAL

5.1 Subject Inclusion Criteria

1. Otherwise healthy, 6 mo-49 years old volunteers
2. Willing to complete the informed consent process (including assent for minors 7-17 years old).
3. Availability for follow-up for the planned duration of the study.
4. For parents of children 6 months – 4 years of age: Willing to participate in the study annually for up to 5 years (if yes, consider for annual return groups).
5. Acceptable medical history by review of inclusion/exclusion criteria and vital signs.
6. Influenza vaccine-naïve or only one prior season of flu immunization with IIV (does not apply to Groups F and G).

5.2 Subject Exclusion Criteria for Enrollment and Subsequent Annual Vaccinations

1. Prior off-study vaccination with the current year's seasonal influenza vaccine
2. Receipt of LAIV in the prior season (does not apply to Groups F and G)
3. Received flu immunizations in 2 or more prior flu seasons (does not apply to Groups F and G)
4. Allergy to egg or egg products, or to vaccine components, including gentamicin, gelatin, arginine or MSG (if will be given LAIV4)
5. Life-threatening reactions to previous influenza vaccinations
6. Asthma in adults. Children aged 2 through 4 years who have asthma or who have had a wheezing episode noted in the medical record within the past 12 months, or for whom parents report that a health care provider stated that they had wheezing or asthma within the last 12 months [If yes, not eligible for LAIV Groups A, B, C, & F].
7. Active systemic or serious concurrent illness, including febrile illness on the day of vaccination
8. History of immunodeficiency (including HIV infection)
9. For children or adolescents through 17 years of age: receiving aspirin therapy or aspirin-containing products [If yes, not eligible for LAIV Groups A, B, C, and F].
10. Known or suspected impairment of immunologic function, including, but not limited to, clinically significant liver disease, diabetes mellitus treated with insulin, moderate to severe renal disease, or any other chronic disorder which, in the opinion of the investigator, might jeopardize volunteer safety or compliance with the protocol.
11. Blood pressure >150 systolic or >95 diastolic at first study visit and the day of vaccination (for children 12 yrs and older, and adults).
12. Hospitalization in the past year for congestive heart failure or emphysema.
13. Chronic Hepatitis B or C
14. Recent or current use of immunosuppressive medication, including systemic glucocorticoids (corticosteroid nasal sprays and topical steroids are permissible in all groups; inhaled steroid use is not permissible)
15. Persons who care for severely immunosuppressed persons who require a protective environment should not receive LAIV, or should avoid contact with such persons for

- 7 days after receipt, given the theoretical risk for transmission of the live attenuated vaccine virus to close contacts. [If yes, may be ineligible for Groups A,B, C and F].
16. Malignancy, other than squamous cell or basal cell skin cancer (includes solid tumors such as breast cancer or prostate cancer with recurrence in the past year, and any hematologic cancer such as leukemia).
 17. Autoimmune disease (including rheumatoid arthritis treated with immunosuppressive medication such as Plaquenil, methotrexate, prednisone, Enbrel) which, in the opinion of the investigator, might jeopardize volunteer safety or compliance with the protocol
 18. History of blood dyscrasias, renal disease, or hemoglobinopathies requiring regular medical follow up or hospitalization during the preceding year
 19. Use of any anti-coagulation medication such as Coumadin or Lovenox, or anti-platelet agents such as aspirin (except up to 325 mg. per day), Plavix, or Aggrenox must be reviewed by investigator to determine if this would affect the volunteer's safety.
 20. Has taken an influenza antiviral medication within 48 hours prior to study vaccination [If yes, may not eligible for LAIV Groups A, B, C and F if unable to reschedule study vaccination].
 21. Receipt of blood or blood products within the past 6 months or planned used during the study
 22. Medical or psychiatric condition or occupational responsibilities that preclude participant compliance with the protocol
 23. Receipt of inactivated vaccine 14 days prior to study enrollment, or planned vaccinations prior to completion of last study visit
 24. Receipt of live, attenuated vaccine within 60 days prior to enrollment of planned vaccination prior to completion of last study visit
 25. Need for allergy immunization (that cannot be postponed) during the study period
 26. History of Guillain–Barré syndrome
 27. Pregnant woman
 28. Breastfeeding [If yes, not eligible for LAIV Group F]
 29. Use of investigational agents within 30 days prior to enrollment or planned use during the study
 30. Donation of the equivalent of a unit of blood within 6 weeks prior to enrollment or planned donation prior to completion of the last visit
 31. Any condition which, in the opinion of the investigator, might interfere with volunteer safety, study objectives or the ability of the participant to understand or comply with the study protocol.

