7 STUDY SCHEDULE

7.1 Screening

Volunteers will be contacted by phone prior to the first study visit. Study staff will briefly review the eligibility criteria, participant availability and the study procedures. If the participant is eligible and interested, the volunteers will be assigned to groups based on, age, inclusion exclusion criteria and availability for annual return vs single year participation.

7.2 Day 0; Enrollment/Baseline/Immunization for all Groups; annually for Groups A and D.

- Adult participants or parents of the volunteer will be provided with a verbal description of the study (purpose and study schedule and procedures). They then will be asked for any questions and to read/sign the consent form (in the first year only). Minor children ages 7-17 years will be given an assent at enrollment. The consent form will be signed prior to the performance of any study procedures. The study staff will discuss with the volunteer or volunteer's parent of their study eligibility criteria and concomitant medication use.
- Obtain vital signs (oral temperature, pulse, and respiratory rate), height and weight. Obtain blood pressure for volunteers 12 years and older.
- Collect blood samples (**except Group C**) as follows:

For blood volumes ≥ 20 mL, collect one 5 mL gold top tube (serum), one 2.5 mL PAXgene tube and one 2.5 mL heparinized, green top tube (CyTOF sample). The remainder of the blood sample will be collected in heparinized, green top tubes. Blood volumes <20 mL will be collected in heparinized, green top tubes only.

- For children weighing more than 100 lb., and from adults, total volume not to exceed 70 mL
 - From children weighing 66-100 lb: total volume not to exceed 30 mL
 - From children weighing 61-65 lb: total volume not to exceed 25 mL
 - From children weighing 41-60 lbs: total volume not to exceed 20 mL
 - From children weighing 16-40 lbs: total volume not to exceed 10 mL
 - From children 6 months through 35 months old, regardless of weight: Obtain a 4 mL blood sample into a heparin (green top) tube.
- All volunteers will be administered the seasonal flu vaccine according to the group assignment. Unless there is a different recommendation from the ACIP in a given year, Group A, B, C and F will receive intranasal spray of LAIV4. Group D, E and G

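### Items 2 and 3 of Section 5.2, read literally with study doses counted, conflict with the annual revaccination planned for Groups A and D

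*Combined protocol and SAP*

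**What the plan says.** The heading of Section 5.2 sets the scope of the whole list: "Subject Exclusion Criteria for Enrollment and Subsequent Annual Vaccinations". Three vaccine-history items matter here:

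- Item 1: "Prior off-study vaccination with the current year's seasonal influenza vaccine".
- Item 2: "Receipt of LAIV in the prior season (does not apply to Groups F and G" (the bracket closes there).
- Item 3: "Received flu immunizations in 2 or more prior flu seasons (does not apply to Groups F and G" (likewise).

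Inclusion 6 in Section 5.1 admits to Groups A to E children who are vaccine-naive or have had one earlier season of inactivated vaccine (IIV).

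The Protocol Summary and Section 4 ask Groups A and D, up to six children each, to come back every year for vaccination and blood sampling. Inclusion 4 puts this at up to 5 years. Section 7.2 is headed "Enrollment/Baseline/Immunization for all Groups; annually for Groups A and D". It gives Group A the live vaccine (LAIV4) unless ACIP advice for that year differs. The Appendix A footnote moves Group D children from IIV4 to LAIV4 at age 2 unless a contraindication develops. Within Section 7.2 the signing of consent is confined to one year, "read/sign the consent form (in the first year only", but the discussion of eligibility at the same visit is not.

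**The concern.** Annual revaccination is what distinguishes Groups A and D from the single-year groups. A study dose of LAIV4 is receipt of LAIV, and a study season is a season of immunization. On their face, therefore, items 2 and 3 turn the planned treatment in one year into a reason for exclusion in the next. Section 5.3.2 does not settle the matter, because it speaks of withholding vaccine only at the first visit.

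The multi-season data are at stake. Summary primary objective 3 concerns the B-cell repertoire after repeated LAIV4, and Summary primary objective 5 concerns IIV followed by repeated LAIV4. Section 3.1 places this topic under secondary objective 2. The annual-return children are the only source of such data. Section 9 says the sponsor will not monitor the study, so sponsor monitoring would not pick up uneven handling between children.

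**Working it through.** The plan gives no figure on this point to reproduce. The check sets the passages side by side and then applies the two items as written.

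**1. Whom the items reach at returns.** Only Groups A and D have annual vaccinations after enrollment. Groups F and G take part for a single year, so exempting them changes nothing at a return visit.

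**2. Whether the items limit themselves.** Item 1 is limited to off-study vaccine. The look-back in items 29 and 30 is tied to enrollment: "Use of investigational agents within 30 days prior to enrollment or planned use during the study" and "Donation of the equivalent of a unit of blood within 6 weeks prior to enrollment". Items 2 and 3 carry neither limit.

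**3. The rule, with study doses counted.** Let p be the seasons of vaccination before entry (0 or 1, from inclusion 6) and r the return number. Five seasons give four returns, r = 1 to 4. If every season is vaccinated, p + r seasons lie behind the child at return r.

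- Item 3 is met when p + r ≥ 2: from r = 2 if naive at entry, from r = 1 with one prior season.
- Item 2 is met when the preceding season's vaccine was LAIV. On the planned vaccine this is every return in Group A. In Group D it is every return after the first LAIV4 season.

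Items met at each return, with vaccine as planned and 12-month spacing:

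| Group and history at entry | r=1 | r=2 | r=3 | r=4 | Conflicts |
|---|---|---|---|---|---|
| A, naive | 2 | 2, 3 | 2, 3 | 2, 3 | 4 of 4 |
| A, one prior season | 2, 3 | 2, 3 | 2, 3 | 2, 3 | 4 of 4 |
| D, naive, entry 12–23 months | none | 2, 3 | 2, 3 | 2, 3 | 3 of 4 |
| D, naive, entry 6–11 months | none | 3 | 2, 3 | 2, 3 | 3 of 4 |
| D, one prior season, entry 12–23 months | 3 | 2, 3 | 2, 3 | 2, 3 | 4 of 4 |
| D, one prior season, entry 6–11 months | 3 | 3 | 2, 3 | 2, 3 | 4 of 4 |

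**4. The ACIP proviso.** If IIV replaces LAIV4 in one season, item 2 is not met at the next return. Item 3 ignores vaccine type, so it alone still gives at least 3 of 4 (naive) or 4 of 4 (one prior season). A naive Group A child given IIV in season 1, for example, has 3 of 4.

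**5. Objectives, if barred doses are withheld and none is given off study.**

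- Summary objective 5: taking repeated LAIV4 to mean at least two LAIV4 seasons, IIV and then LAIV4 twice needs three vaccinated seasons. At the third, two lie behind the child and item 3 applies. No child can follow this sequence.
- Summary objective 3: item 2 rules out LAIV4 in consecutive seasons. A naive Group A child is barred in season 2, passes both items in season 3 (one earlier season, none in the season just past), and is barred afterwards by item 3. LAIV4 in seasons 1 and 3 remains possible, with Day 0 and Day 6–8 blood each time. With one prior season, only one LAIV4 season is possible. A second LAIV4 dose within a season does not fill the gap, because Section 7.6.1 and Appendix A schedule no Group A blood at or after Dose 2 in that season.
- Section 3.1 secondary objective 2: partly met. A naive Group D child can still have IIV4 and then LAIV4 if aged 24 months by the first return. At 12-month spacing that means entry at 12–23 months. If returns fall anywhere in August to December (an assumption; the Summary gives that window for enrollment), spacing runs from about 7 to 17 months, and the entry-age boundary from 24 − 7 = 17 down to 24 − 17 = 7 months.

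**6. Scope.** Groups A and D: 6 + 6 = 12. Maximum enrollment: 6 + 20 + 20 + 6 + 20 + 40 + 40 = 152.

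**The case against.** The strongest reply is that nobody would read the items this way. Items 23 and 24 also exclude planned vaccination before the last study visit, with no off-study limit. Taken literally, they would shut out children scheduled for a second study dose, which cannot be meant. Unqualified vaccine wording in this list can therefore mean non-study vaccine. Inclusion 6 and the exemption of Groups F and G point another way, to history at entry. The passages written specifically for Groups A and D all call for revaccination.

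This stands as evidence of intent, and the documents give no ground for predicting that staff would turn these children away. It does not remove the inconsistency, because it leaves two candidate meanings with different results. Take a child who misses a study season, receives LAIV off study and returns the next season. If item 2 screens only history at entry, it does not exclude the child. If it covers non-study vaccine at any visit, it does. Item 1 cannot decide, since it concerns only the current year's vaccine.

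A reader might also infer that staff commit a deviation whichever way they act. The documents do not go that far. Vaccinating departs from the literal words of Section 5.2, and Section 14.6 counts any noncompliance as a deviation. But Section 5.3.1 makes vaccination conditional on eligibility, and the annual-return text says only that participants will be asked back. Withholding vaccine from a child who meets a listed exclusion is not clearly a deviation.

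**Conclusion.** The inconsistency is real and lies in the wording. Section 5.2, read literally with study doses counted, contradicts the annual-return plan in the Summary, Section 4, Section 7.2 and Appendix A.

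The counts of 4 of 4 (Group A on LAIV4) and 3 or 4 of 4 (Group D) hold for a child who enters in the first season and is vaccinated in all five. If all 12 children did so, 24 + (18 to 24) = 42 to 48 of 48 returns would conflict on the planned vaccines, and at least 18 + 18 = 36 under any ACIP sequence. A reader might take these totals as the expected loss. They describe full first-season entry and full return, whereas the plan allows up to six children per group, entry in each of 5 years and participation of up to 5 years. A child who enters in the last season has no return. A naive Group A child who skips season 2 meets neither item in season 3.

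A reader might also conclude that the repeated-LAIV4 objective is lost or that the main results are compromised. Neither follows. Summary objective 3 would be partly met, and the loss of Summary objective 5 arises only under literal application. The Section 3.1 primary objectives and all first-year data are untouched, and Section 10.1 describes the study as exploratory. The point merits a short amendment because the affected children are the only ones followed over several seasons.

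**What to change.** Amend Section 5.2 so that items 2 and 3 are reconciled with the annual-return plan. For Group A and D return visits, state:

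- whether each item applies;
- whether vaccine given in this study counts toward it;
- how vaccine received off study between seasons is treated.

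The choice of rule belongs to the investigators and the sponsor; the need is that the passages agree. The cost is one or two sentences by amendment, with no added participants, visits or procedures.

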Group A (LAIV4/annual return): Up to six 2-4 year old volunteers will be given a quadrivalent live, attenuated influenza vaccine (LAIV4). Blood samples to conduct the assays described will be taken at Day 0 pre-immunization and Day 6-8 post-Dose 1 for all children irrespective of those who require 1 dose (prior flu vaccination history) or 2 doses (vaccine-naïve). For children requiring 2 doses of vaccine, a second immunization will be given at Day 28-32 after Dose 1. All participants in this group will be asked to return annually for repeat immunization per ACIP guidelines and blood sample collection.

Group B (LAIV4/single year): Up to twenty 2-4 year old volunteers will be given a quadrivalent live, attenuated influenza vaccine (LAIV4). Blood samples to conduct the assays described will be taken at Day 0 pre-immunization and Day 6-8 post-Dose 1 for all children irrespective of those who require 1 dose (prior flu vaccination history) or 2 doses (vaccine-naïve). For children requiring 2 doses of vaccine, a second immunization will be given at Day 28-32 after Dose 1.

Group C (LAIV4/NP swab group/single year): Up to twenty 2-4 year old volunteers will be given a quadrivalent live, attenuated influenza vaccine (LAIV4). NP swabs will be collected at Day 1 and Day 20-22 post-Dose 1 for all children irrespective of those who require 1 dose or 2 doses of vaccine. For children requiring 2 doses of vaccine, a second immunization will be given at least 28 days after Dose 1. No blood will be collected for this group.

Group D (IIV4/annual return): Up to six 6 month-23 month old (inclusive) volunteers will be given a quadrivalent inactivated influenza vaccine (IIV4). Blood samples to conduct the assays described will be taken at Day 0 pre-immunization and Day 6-8 post-Dose 1 for children requiring 1 dose of vaccine (prior flu vaccination history). For children requiring 2 doses of vaccine (vaccine-naïve), a second immunization will be given at Day 28-32 after Dose 1. The second blood sample will be collected on Day 6-8 post-Dose 2. Volunteers will be asked to return annually for repeat immunization per ACIP guidelines and blood sample collection.

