will be vaccinated with IIV4. Children who are vaccine-naïve will receive their Dose 1 of their vaccine at this visit. Volunteers will be observed in clinic for 15 minutes for any immediate serious reactions. Vaccine-naïve volunteers requiring Dose 2 will return at least 28 days post-Dose 1.

- A Memory Aid will be given to the volunteers/volunteer's parent with written and oral instructions for collection of information about serious adverse events. The memory aid is a simple diary for volunteer to record change in a health status and medications between study visits.
- The schedule for subsequent study visits will be reviewed.

7.3 Day 1 post- Dose 1 immunization for Group C and Group F only

- Review of medications and memory aid for serious adverse events
- Collect nasopharyngeal swab specimen; no blood sample will be collected at this visit.
- The schedule for subsequent study visits will be reviewed.

7.4 Day 6-8 post-Dose 1 immunization except Group C and vaccine-naïve volunteers in Group D and Group E requiring Dose 2; annually for Groups A and D.

- Review of medications and memory aid for serious adverse events
- Collect blood samples as follows:

All blood samples will be collected in heparinized, green top tubes to be picked up by the [name] lab for processing and analysis. For sample volumes >30 mL, one heparinized, green top tube will be sent to the HIMC if available ([name] lab requires at least 30 mL in heparinized, green top tubes at Day 6-8).

- For children weighing more than 100 lb., and from adults: total volume not to exceed 70 mL
 - From children weighing 66-100 lb: total volume not to exceed 30 mL
 - From children weighing 61-65 lb: total volume not to exceed 25 mL
 - From children weighing 41-60 lbs: total volume not to exceed 20 mL
 - From children weighing 16-40 lbs: total volume not to exceed 10 mL
 - From children 6 months through 35 months old, regardless of weight: Obtain a 4 mL blood sample into a heparin (green top) tube.
- The schedule for subsequent study visits will be reviewed for, Group F and G

- This will be the final visit for volunteers with prior influenza vaccination history in Group A, B, D and E. Complete Study Status form and Study Reimbursement form for these volunteers.

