Appendix A. Schedule of visits

Appendix B. Schedule of events

Appendix C. Season-specific FluMist Quadrivalent package inserts 2014-2018

Appendix D. Season-specific Fluzone Quadrivalent package insert 2014-2018

APPENDIX A: SCHEDULE OF VISITS

Groups	Naïve /prior vacc	Day 0	Day 1 Post-Dose 1	Day 6-8 Post-Dose1	Day 21 Post-Dose1	Day 28-32 post-Dose 1 (for Dose 2) Day 28 ± 4 Post-Dose 1 (blood draw, NP Swab)	Day 6-8 Post-Dose 2
Group A 2-4 yo Annuals	naive	LAIV4 Dose 1/ Blood	--	Blood	--	LAIV4 Dose 2	--
	Prior vacc	LAIV4/Blood	--	Blood	--	--	--
Group B 2-4 yo Single yr	Naive	LAIV4 Dose 1/ Blood,	--	Blood	--	LAIV4 Dose 2	--
	Prior vacc	LAIV4/Blood	--	Blood	--	--	--
Group C 2-4 yo Single yr	Naive	LAIV4 Dose 1	NP Swab	--	NP Swab	LAIV4 Dose 2	--
	Prior vacc	LAIV4	NP Swab	--	NP Swab	--	--
Group D 6-23mo Annual	Naive	IIV4* Dose 1/ Blood	--	--	--	IIV4* Dose 2	Blood
	Prior vacc	IIV4*/ Blood	--	Blood	--	--	--
Group E 6-23mo Single yr	Naive	IIV4 Dose 1/ Blood	--	--	--	IIV4 Dose 2	Blood
	Prior vacc	IIV4/ Blood	--	Blood	--	--	--
Group F 9-13 yo 18-49 yo	Prior vacc	LAIV4, blood	NP Swab	Blood	--	Blood, NP Swab	--
Group G 9-13 yo 18-49 yo	Prior vacc	IIV4, blood	--	Blood	--	Blood	--

* When these children turn 2 yrs old in annual f/u, they will be switched to receive LAIV4 vaccine unless they develop a contraindication.

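### The LAIV4 exclusions for wheeze, aspirin and recent antivirals are set by group letter and omit Group D, which moves to LAIV4 from age 2

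*Combined protocol and SAP*

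**What the plan says.** By its title, Section 5.2 covers both enrollment and the later annual vaccinations, so it is the list in force when Group D children return.

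- **Item 6** (asthma, or wheeze in the past 12 months, in children aged 2 through 4) ends "had wheezing or asthma within the last 12 months [If yes, not eligible for LAIV Groups A, B, C, & F".
- **Item 9** (aspirin, through age 17) ends "If yes, not eligible for LAIV Groups A, B, C, and F".
- **Item 20** (influenza antiviral within 48 hours) is conditional: such a volunteer "may not eligible for LAIV Groups A, B, C and F if unable to reschedule study vaccination".
- **Item 15** (carers of severely immunosuppressed persons) has similar lettering, but its body refers to the product: such persons "should not receive LAIV, or should avoid contact with such persons for" 7 days.
- **Item 4** (allergy) applies to anyone who will be given LAIV4 and uses no group letters.

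Group D is up to six children who enter at 6-23 months on IIV4 and return each year. The Appendix A footnote says: "When these children turn 2 yrs old in annual f/u, they will be switched to receive LAIV4 vaccine unless they develop a contraindication". Primary objective 5 in the Protocol Summary, on IIV followed by repeated LAIV4, shows that the switch is intended.

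Section 7.2 covers Day 0 and Group D's annual visits: "Unless there is a different recommendation from the ACIP in a given year, Group A, B, C and F will receive intranasal spray of LAIV4". Groups D, E and G "will be vaccinated with IIV4". The switch is not mentioned there.

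**The concern.** Leaving Group D out of the LAIV4 brackets is right at enrollment, when these children receive IIV4. It stops being right at the first annual visit at age 2 or older. From then on Group D receives LAIV4 in the age range that the child clause of item 6 addresses. Groups A, B and C are the other groups given LAIV4 at ages 2-4, and all three are named. Group E leaves after one year.

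Take a 3-year-old with wheeze in the past 12 months. In Group A, item 6 bars LAIV4. In Group D, no item in Section 5.2 states that bar, and the annual-visit procedure still lists the child under IIV4. At stake is a safety eligibility rule for toddlers given a live vaccine, which for this one group depends on inference.

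**Working it through.** **1. Which LAIV4 rules reach Group D after the switch**

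| Section 5.2 item | Tied to | Reaches Group D on LAIV4? |
|---|---|---|
| 4, allergy | product | yes |
| 6, asthma or wheeze | A, B, C, F (firm) | not stated |
| 9, aspirin | A, B, C, F (firm) | not stated |
| 15, immunosuppressed contacts | product in the body, letters in the bracket | yes, by the body text; not counted here |
| 20, antiviral | A, B, C, F (conditional) | not stated |

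**2. What else could stop the vaccination**

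- The footnote excepts a contraindication. The protocol text does not define the word or point to Section 5.2, and the verb used leaves a pre-existing condition unclear.
- The Protocol Summary says of Group D: "Volunteers will be asked to return annually for repeat immunization per ACIP guidelines and blood sample collection". Section 7.2 also defers to a differing ACIP recommendation. That guidance is not reproduced.
- Section 6.1.2 and Appendix C attach the season's FluMist inserts. They were not available for this review, so their content is unknown.
- Section 5.3.1 gives vaccine by eligibility and group, which leads back to the same lettered items.
- Item 7 covers illness on the day. Item 14 catches wheeze only through steroid use. Items 10 and 31 rest on judgement.
- Section 6.4 records medication at each visit. Its list for investigator consultation exempts aspirin up to 325 mg per day, as item 19 does, and names no antiviral. Item 9 has no dose threshold.

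None of the text available states the item 6 or item 9 bar for Group D.

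**3. How many vaccinations are involved**

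Inputs from the documents: six children at most, entry at 6-23 months, enrollment in each of 5 years, LAIV4 from 24 months. Assumptions: one season every 12 months, full return, and no season after study year 5.

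LAIV4 seasons at ages 2-4 per child, by year of enrollment:

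| Entry age | Yr 1 | Yr 2 | Yr 3 | Yr 4 | Yr 5 | Mean |
|---|---|---|---|---|---|---|
| 6-11 months | 3 | 2 | 1 | 0 | 0 | 6/5 = 1.2 |
| 12-23 months | 3 | 3 | 2 | 1 | 0 | 9/5 = 1.8 |

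- Ceiling, all six enrolled in year 1: 6 x 3 = 18.
- Enrollment even over years and months of age: (6 x 1.2 + 12 x 1.8)/18 = 1.6 per child, and 6 x 1.6 = 9.6.
- Items 9 and 20 also apply at age 5. Only a child who entered at 12-23 months in year 1 reaches a season at that age. This adds at most 6 (18 + 6 = 24), or 12/18 x 1/5 x 6 = 0.8 with even enrollment (9.6 + 0.8 = 10.4).

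These counts set aside items 2 and 3, which exclude LAIV in the prior season and immunization in two or more prior seasons. Applied literally to returnees, they leave one LAIV4 season: the first return of a child who entered vaccine-naive at 12-23 months in years 1-4. That is at most 6 x 1 = 6, or 12/18 x 4/5 x 6 = 3.2 with even enrollment if all are vaccine-naive at entry.

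**4. Children on LAIV4 in any one season (even enrollment, items 2 and 3 set aside)**

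Each year brings 6/5 = 1.2 children: 0.4 aged 6-11 months and 0.8 aged 12-23 months. The expected numbers on LAIV4 at ages 2-4 in study years 1-5 are 0, 0.8, 2.0, 3.2 and 3.6, which sum to 9.6. The peak is 3.6, in year 5.

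**The case against.** The strongest reply is that this is a missing cross-reference and nothing more. The only sentence that gives Group D LAIV4 carries its own stop. In a protocol that attaches the label of a licensed vaccine, the label and the LAIV conditions already in Section 5.2 are the natural meaning of contraindication. Item 4 and the body of item 15 already follow the product, and the requirement to be otherwise healthy and the investigator's judgement also apply. If items 2 and 3 are read sensibly so that returning children can have repeated LAIV4, items 6 and 9 deserve the same sensible reading.

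Much of this stands. A reader might infer that the protocol instructs staff to give LAIV4 to a child with recent wheeze. It does not: the footnote excepts a contraindication, and the inserts may state the same restriction. A reader might also infer a probability that some child is harmed. The documents give no wheeze rate, so no such figure should be quoted, and the counts above are vaccinations given without a named bar. Nor should 18 be read as the only answer, since it depends on how items 2 and 3 are taken.

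What does not fall is the asymmetry. Careful staff would probably reach the right decision, but in Group A the rule tells them and in Group D they must infer it.

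**Conclusion.** The point holds as a gap in stated eligibility. Items 6 and 9, and conditionally item 20, are not stated for Group D once it receives LAIV4, although Section 5.2 governs those visits. The other safeguards are real but partial, and the FluMist inserts could not be checked.

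At most six children are affected. The range of 3.2 to 18 vaccinations at ages 2-4 reflects the enrollment pattern and the reading of items 2 and 3. The upper readings assume full return, and 3.2 also assumes that every child enters vaccine-naive. No sample size, analysis or other statistical figure changes. The severity is minor to should-fix: a small gap, worth closing because it concerns the safety of young children and costs almost nothing.

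**What to change.** - **Items 6 and 9:** word the bracket by product, for example *If yes, not eligible to receive LAIV4 (Groups A, B, C and F, and Group D once switched to LAIV4)*.
- **Items 15 and 20:** add *and Group D once switched to LAIV4*, keeping their conditional wording.
- **Appendix A footnote:** end it with *unless they have a contraindication, including any LAIV4 exclusion in 5.2*.
- **Section 7.2:** state that Group D children aged 2 or over receive LAIV4 at annual visits, subject to that footnote.

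This is a wording amendment with no new procedures, and eligibility in Groups A, B, C and F does not change. The cost is that an occasional Group D child is not switched in a given season, an outcome the footnote already allows for. One such child is 1/6 = 17% of that season's IIV-then-LAIV4 data if six are on LAIV4, and 1/3.6 = about 28% at the even-enrollment peak for ages 2-4. Counting the 0.8 expected at age 5 in that year, it is 1/4.4 = about 23%.
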